5.7.2 Clinical laboratory

The following laboratory safety data are collected for this study:

Haematology	Chemistry	Urinalysis
Hemoglobin	Sodium	Leukocytes
Erythrocytes	LDH (Lactate dehydrogenase)	Nitrite
Hematocrit	Potassium	Urobilinogen
Thrombocytes	Creatinine	Protein
Leukocytes	Serum bilirubin level	pH
	AST (Aspartate aminotransferase)	Occult blood (erythrocytes, leucocytes)
	ALT (Alanine aminotransferase)	Specific gravity
	Urea	Ketones
	ALP (Alkaline phosphatase)	Bilirubin
	FSH (Follicle-stimulating hormone) (for postmenopausal women only)	Glucose

Laboratory safety data for haematology, biochemistry and urinalysis will be summarized using descriptive statistics and listed per visit, using protocol visits. Change from baseline will be calculated and presented as well for quantitative data, using the same summary statistics. If applicable, laboratory safety data collected as additional/unscheduled assessments (i.e. apart from those per protocol) will only be listed and will not be used in summary statistics.

Baseline is defined as the Visit 2 measurement. In case the Visit 2 measurement is missing, the Visit 1 measurement will be used.

For laboratory safety data, all recorded and determined laboratory safety data will be listed, including information on the reference ranges, if available. In addition, information regarding age at screening and sex will be added to the listing.

All safety laboratory parameters will be presented in the tables and listings in the same standard units as supplied, which will be SI units.

Lastly, for clinical laboratory parameters, a listing will be created presenting all data that are out of reference range on a per-patient level, including any available unscheduled measurements. Note that clinical significance for out-of-range values is not collected per eCRF and can therefore not be presented. Information regarding age at screening and sex will be added to this listing. The SAF population is used for the presentations.

5.7.3 Vital Signs

Vital sign data consist of measurements for pulse rate and systolic/diastolic blood pressure (sitting). Vital signs will be summarized and listed per visit (protocol visits). Change from baseline will be calculated and presented as well, using the same summary statistics. Visit 2 is considered the baseline visit for vital signs; in case Visit 2 is missing, the Visit 1 measurement will be used as baseline instead. If applicable, vital sign measurements collected as additional/unscheduled assessments (i.e. apart from those per protocol) will only be listed and will not be used in summary statistics. The SAF population is used for the presentations.

5.7.4 Electrocardiography (ECG)

ECG outcome results (corrected QT interval and normal/abnormal result) will be presented descriptively per protocol visit. If applicable, ECG measurements collected as additional/unscheduled assessments (i.e. apart from those per protocol) will only be listed and will not be used in summary statistics. The SAF population is used for the presentations.

5.7.5 Prior and concomitant medication/therapies

The use of prior and concomitant medication/therapies will be listed for all subjects: included will be the preferred term, World Health Organization (WHO) coding information and the Anatomic Therapeutic Chemical (ATC) class code), dose, route of administration, start and stop date, frequency and reason for administration, as well as information if given for an AE. Differentiation will be made between prior and concomitant medication/therapies, by creating two separate listings. A frequency table per ATC class code and WHO drug code will be created if considered relevant, separately for prior and concomitant medication/therapies. The SAF population is used for the presentation.

5.8 Scheduled visits, dosing, and treatment compliance

5.8.1 Visit dates

A listing with actual visit dates (and times, if applicable) per patient will be presented.

5.8.2 Dosing and treatment compliance

Relevant dosing information (first dosing date, last dosing date), scheduled and actual dosing dates/times and treatment compliance information will be determined and listed for each patient. Summary statistics for the number of N-Acetyl-L-Leucine doses taken during the

Parent study phase, based on bottles/sachets of dispensed and returned unused bottle/sachets counts, will be calculated. Compliance is defined as 100% * (total number of IB1001 bottles and/ or sachets dispensed – total number of IB1001 unused bottles and/ or sachets returned), divided by the number of bottles which should have been used. Note that the number of bottles and/ or sachets the patients should have used depends on the dosage they should take (see Section 2.3 for reference) and the duration of the treatment period. Considering the fact that the patient's total daily dose may be reduced by up to half of their assigned dose at the discretion of the investigator, the actual dose will be used to determine the correct compliance calculation, if collected in the eCRF. The proportion of patients who take at least 80% of the prescribed medication will also be shown. Total dosing period is defined as the duration (in days) between first dose date and last dose date.

6 EXTENSION PHASE: STATISTICAL ANALYSIS

6.1 General considerations

The Extension phase is considered the study period starting with the Extension phase baseline (Visit 7) until Visit 12. In principle, data presentations will be created for the full Extension phase. Only where applicable and relevant, a separation will be made as follows:

- Extension phase I: Extension phase Visit 7 until Visit 10
- Extension phase II: Extension phase Visit 10 until Visit 12.

All evaluations will be exploratory in nature, and all endpoints for the Extension Phase are considered secondary to the endpoints of the Parent Study. Statistical analysis will only be applied for some of the endpoints as defined for Extension phase I, no statistical analyses will be done for the endpoints in Extension phase II.

Summary presentations and listings will be presented and only reported data will be presented (i.e. no imputation or LOCF will be done) for data collected during Extension phase II. If not otherwise defined, data will be presented as missing where applicable.

Raw data (in listings) will be presented in the same precision as received. Appropriate rounding will be performed for the following summary statistics, where applicable: mean, standard deviation (SD) and two-sided 90% confidence limits will be presented with at least one more decimal than the original data; minimum and maximum values will be presented with the same precision as the original data. In frequency tables, percentages will be presented with 1 decimal unless otherwise stated.

P-values will be presented with 3 decimals, and those smaller than 0.001 will be replaced by <0.001. One-sided p-values smaller than 0.05 will be considered statistically significant for the primary endpoint and indicative for other endpoints. No adjustment for multiple comparisons will be applied. Conclusions regarding treatment efficacy will not solely rely on detecting statistical significance but equal emphasis will be placed on the magnitude and clinical relevance of treatment differences as judged by the point estimates.

Descriptive statistics presented in general summary tables will be the number of non-missing observations (n), mean, SD, minimum, median and maximum for quantitative data. For categorical data, frequency counts and percentages will be determined.

For the full Extension Phase, the measurement at Visit 7 is considered the baseline. In case of missing Visit 7A data for safety measurements (e.g. for safety lab), and Visit 7B has occurred within 1 (+6) days of Visit 6, the Visit 6 data from the Parent Study should be used instead (data are not being re-entered in the database): see also Section [2.2.2](#) for clarification. No screen failures will be present in the data.

No screen failures will be present in the data.

For the full Extension Phase, a treatment emergent adverse event (TEAE) is defined as an adverse event (AE) that appears during or after the start of study treatment in the Extension Phase at Visit 7B and was absent before. As a consequence, AEs occurring during the washout phase between Visit 9 and Visit 10 will also be considered treatment emergent.

6.2 Adjudication of endpoint data

Videos of the primary and non-primary anchor tests are collected throughout the extension phase for the CI-CS. These videos may be analyzed in order to inform the development and validation of the CI-CS but will not be reported in the CSR (and hence not listed or tabulated). Data received will be included as-is in the CDISC files. In case of analysis, the following process applies: For the CI-CS assessments of both the primary and non-primary anchor tests, after a patient completes Visit 10 of the Extension phase, the independent raters will be given 3 video pairs of from Visit 7 to Visit 9, Visit 9 to Visit 10, and Visit 7 to Visit 10. After a patient completes Visit 12 of the Extension phase, the independent raters will be given a video pair from Visit 10 to Visit 12 (the raters may also assess additional video pairs, i.e. Visit 1 to Visit 12, on an exploratory basis). The videos will be presented in a random order, and the independent raters will be blinded to the timepoint corresponding to each video. The appropriate Likert scale score will be provided to each of the videos and pairs of videos. For further details regarding scoring and adjudication, which will be similar to that of the Parent study, see Section [5.2](#).

6.3 Missing data

Data from withdrawal patients will be included in the analysis until their last assessment.

For handling missing data in the Extension Phase, similar approaches as described in Section [5.3](#) will be followed, with the alteration that “first dose date” is the first dosing of the Extension Phase. For AE and concomitant medication this indicates that events started during the Parent Study and continuing during the Extension Phase will be considered prior for the Extension Phase.

6.4 Interim analysis

Per patient data listings and summary tables/plots will be provided for several DSMB meetings as specified in the DSMB Charter created for the Parent study.

The final CSR will be written upon the completion of the full Extension phase, and no interim analysis is performed during the Extension phase.

6.5 Baseline characteristics

6.5.1 Inclusion/exclusion criteria

An individual patient listing of the deviations from inclusion criteria will be presented. No exclusion criteria are collected for the Extension Phase, and no separate inclusion is done for Extension phase II.

6.5.2 Demographics

Demographic data at baseline will be summarized for all patients and by the 4 age/weight/dosing groups (using Visit 7 information) in tabulations, even if there is a change in dose between Visit 7 and 8, or between Visit 8 and 10, or Visit 10 and 11 (see Section 2.3.2).

Appropriate descriptive statistics² for age, height, weight, BMI, ethnic group and sex will be given. The summary will be created for each analysis population separately. Additionally, demographic data will be listed.

6.5.3 Baseline characteristics

The following relevant patient baseline characteristics will be listed and summarized overall (frequency and percentage) and are considered key subgroups, and will only be used for presentations of the primary endpoint in Extension phase I analyses:

- Naïve versus non-naïve, as determined at screening during the parent study
- Age (paediatric versus adult) at Visit 7
- Gender (male versus female)
- Age/weight/dosing group as applicable at Visit 7
- Selected Primary Anchor Test (9HPT-D or 8MWT) as defined during the parent study
- Patients on miglustat vs Patients not on miglustat at Visit 7
- Composite of SARA Subtests 1- 4 (Gait, Stance, Sitting, Speech): classification based on below (\leq)/above the median value at Visit 7
- Composite of modified (5 domain) NPC-CSS score: classification based on below (\leq)/above the median value at Visit 7
- ASIS: classification based on below (\leq)/above the median value at Visit 7
- Age of diagnosis: Early-infantile (<2 years), Late-infantile (2 to < 6 years), Juvenile (6 to < 15 years), Adolescent/Adult (\geq 15 years)
- Disease severity: classification based on NPC-CSS below (\leq)/ above the median score at Visit 7.

6.5.4 Disposition

A summary table will be created, stating the number of patients per site, including site number, location/country, and investigator.

² Only present descriptive statistics and listings for those demographics data that are collected during the Extension Phase.

To present disposition, a summary of all included, treated, and completed patients will be created for the Extension phase I and II separately, and for the full Extension phase.

Additionally, in the same summary, the number/percentage of patients in the SAFe and mITTe will be presented. Furthermore, the frequency and percentage per reason for non-completion will be added.

A listing displaying all disposition information (including reasons for withdrawal and reasons for exclusion from the analysis population, if available electronically) on a per patient level will be created. This listing will include follow-up time for each patient, calculated from date of first dose during the Extension Phase until end of Extension phase or withdrawal date.

6.5.5 Medical history

Note that only for patients not having a seamless transition from the Parent study to the Extension phase, additional medical history data may be collected during the intermediate time. Medical history³ will be tabulated per System Organ Class (SOC) and Preferred term (PT) according to the Medical Dictionary for Regulatory Activities (MedDRA) terminology list and presented as number/percentage of patients in each SOC and PT for the SAFe. SOC and PT will be presented in descending order of frequency of occurrence based on SOC and PT. These data will also be listed on a per patient level.

6.5.6 Pregnancy data

Pregnancy test result data will be listed for females of childbearing potential only, on a per visit basis.

6.5.7 Other screening data

Other data collected at screening and/or baseline only, if available, will be listed. These screening/baseline data will be presented using all subjects included in the extension phase, if applicable.

6.6 Statistical analysis efficacy endpoints

The analysis population for all efficacy endpoints is the mITTe.

Analyses of the primary and key secondary endpoints based on the mITTe population will utilise a last observation carried forward (LOCF) approach for missing NPC-CSS scores at Visit 9. For the primary endpoint 5-Domain NPC-CSS this implies that the measurement of Visit 8 will be used instead. Other endpoints will not be imputed, and missing data will be reported as is. No sensitivity analyses will be applied.

For the primary endpoint for the Extension Phase there will be separate descriptive statistical displays within the key subgroups as listed in Section 6.5.3, without any statistical analysis. For the subgroup presentations, only the mITTe population will be used. No plots will be created. All individual primary endpoint data will be listed as well.

³ Only collected medical history between the Parent phase and Extension phase, as the medical history for the Parent phase will already be presented in the interim CSR.

All efficacy endpoints for Extension phase Visit 10 to Visit 12 are considered exploratory, and therefore described under section [6.6.3](#).

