8.5.1 Primary Efficacy Endpoint

The primary endpoint is based on the modified 5-domain NPC-CSS score with success defined as no change or a decrease in the 5-domain NPC-CSS score from Visit 7 to Visit 9.

It is postulated that under standard of care, 90% of patients would worsen (higher score) in terms of their performance in 5-domain NPCS-CSS scale over a 12-month period, while conversely only 10% would show similar performance or some improvement. Statistical evaluation of the primary binary endpoint (success/failure on the 5-Domain

NPC-CSS scale) will compare the proportion of success with 10% in a one-sided Fishers Exact test at the one-sided 5% significance level.

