8.6 Missing Data

Analyses based on the mITTe analysis set will utilize a last observation carried forward (LOCF) approach for a missing video at Visit 9.

For the primary endpoint 5-Domain NPC-CSS endpoint this implies that the score of Visit 8 will be used instead. Other endpoints will not be imputed, and missing data will be reported as is. No sensitivity analyses will be applied.

For all other endpoints there will be no imputation for missing data and data will be reported and evaluated as observed.

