2.2.2 Extension Phase

The (full) Extension phase is considered the study period starting with the Extension phase baseline (Visit 7) until Visit 12. In some instances, however, it may be beneficial to make the following split:

- Extension phase I is considered the study period starting with the Extension phase Visit 7 until Visit 10.
- Extension phase II is considered the study period starting with the Extension phase Visit 10 until Visit 12.

The Extension phase will enroll patients who have completed Visit 6 of the Parent study phase.

During the Extension phase, patients will be assessed 6 times over a 25.5-month period.

Baseline Visit of the Extension Phase

Visit 7 (Part A and B) is the baseline of the extension phase. The assessments (Part A and Part B) comprising Visit 7 may be conducted over a two-day period (“Part A” and “Part B”). If Visit 7B is scheduled 1 day (+6 days) after Visit 6 (Washout 2 of the Parent study), the assessments conducted at Visit 6 should count as Visit 7A (i.e. the assessments do not need to be repeated).

If Visit 7B cannot be scheduled 1 day (+6 days) after Visit 6, the assessments included in Visit 7A and Visit 7B should be performed over two consecutive days, i.e. Visit 7B occurs +1 day after Visit 7A.

In general Visit 7A will be the same as Visit 6 in the Parent phase, or within one week following Visit 6. But a non-seamless transition of several weeks or months is possible. The same subject numbers will be used throughout the Parent and the Extension study phase.

Extension Phase Treatment Period I

From Visit 7B onward, all patients will receive treatment with N-Acetyl-L-Leucine for 365 days (+/-14 days).

Visit 8 will occur at approximately Day 180 (+/-14 days).

Visit 9 (Part A and B) will occur at approximately Day 365 (+/-14 days).

The assessments comprising Visit 9 may be conducted over a two-day period (“Part A” and “Part B”).

Extension Phase Washout Period

After **Visit 9B**, all patients will enter a 42-day (+14 days) washout phase.

Visit 10 will occur at Day 407 (+ 14 days).

Extension Phase Treatment Period II

From **Visit 10** onward, all patients will receive treatment with N-Acetyl-L-Leucine for 365 days (+/-14 days).

Visit 11 will occur at Day 587 (+/-14 days).

Visit 12 will occur at Day 767 (+/-14 days).

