2.4.2 Extension Phase

The sample size is determined by the number of patients that move into this Extension Phase from the Parent Study. The expectation is that between 60% and 70% of patients will rollover into the extension period. With 20 out of 32 patients (62.5%) rolling over, the study will have 80% power to detect an improvement in the success rate to 31% compared to the null hypothesis value of 10%.

Patients who completed Visit 10 of the Extension phase and are willing to continue for an additional year will continue in the Extension Phase until Visit 12.

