5.6 Statistical analysis efficacy endpoints

The primary analysis population is the mITT for the primary and all secondary endpoints. Analyses of these endpoints based on the PPS will also be undertaken to provide supplementary information on efficacy. The ITT population will be used only for baseline summary tables.

Analyses of the primary endpoint based on the mITT population will utilise a last observation carried forward (LOCF) approach for missing/unreadable videos at Visit 5 and Visit 6. For the primary endpoint CI-CS, this implies that the CI-CS value for Visit 4 to Visit 6 will be assigned the value 0 (stable) if both videos at Visit 5 and Visit 6 are unavailable.

Also, for the key secondary endpoint, Change in Severity Score based on Averaged Clinical Impression of Severity (CI-S), it is assumed that if both videos are missing/unreadable for the baseline (Videos from Visit 1 or 2), treatment (Videos from Visit 3 or 4), or washout (Videos from Visit 5 or 6) period, the average change from one period to another will be assigned the value 0 (stable).

A sensitivity analysis for missing data will be performed for the statistical analyses to compare patient's outcome on the primary outcome measure and their compliance throughout the study. The robustness of the primary analyses in the mITT analysis set will be assessed as follows:

- If either video for Visit 3 or Visit 4 is available but both videos for Visit 5 and Visit 6 are not available, then the value -1 (worsening) will be used instead of 0 for the CI-CS for Visit 4 to Visit 6 unless the missingness is due to a technical reason (MCAR, e.g. due to machine failure).

For each of the primary and secondary endpoints there will be separate descriptive statistical displays within the key subgroups as listed in Section 5.5.3 without any statistical analysis. For the subgroup presentations, only the mITT population will be used. Spaghetti plots will not be created for the subgroup analyses; these will be presented in forest plots (one for each endpoint, excluding the SARA -, SAFI - and mDRS subscores and excluding the EQ-5D-5L/Y), presenting the mean or (pseudo-)median with a 90% two-sided CI, using a stem at mean or median difference of 0, where applicable. Upon discretion of the programmer, the forest plots may be presented as two plots: one for Visit 4 versus Visit 2 and one for Visit 6 versus Visit 4.

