6.6.1 Primary endpoint

The Niemann-Pick disease type C Clinical Severity Scale (NPC-CSS) measures disease progression⁴ via clinical signs and symptoms in 9 major (ambulation, cognition, eye movement, fine motor, hearing, memory, seizures, speech, swallowing) and 8 minor/modifier (auditory brainstem response, behavior, gelastic cataplexy, hyperreflexia, incontinence, narcolepsy, psychiatric, respiratory problems) domains. A higher NPC-CSS score indicates a clinical worsening, while a lower NPC-CSS score indicates a clinical improvement. A 0-point change in the NPC-CSS score represents a stabilization of disease progression, which is also considered a significant clinical improvement. In the current study, a 15-domain version of the NPC-CSS has been used which omits the ‘hearing’ major domain, and the ‘auditory brain stem’ minor domain from the full 17-domain scale. A modified (5 domain) NPC-CSS score is limited to the assessment of the following 5 major domains: ambulation, cognition, fine motor, speech, and swallowing.

The primary endpoint in this Extension Phase is success measured on the 5-domain NPC-CSS score from the Extension Phase baseline (Visit 7) to the end of treatment in the Extension Phase (Visit 9). Success is defined as no change or a decrease in the 5-domain NPC-CSS score from Visit 7 to Visit 9.

The primary endpoint will be summarized using a frequency table. The primary statistical analysis of comparing the proportion success with the null proportion of 0.10 will be done using a one-sided Fisher’s Exact Test, expecting an increase in the success rate. The statistical result (one-sided p-value and exact 90% confidence interval⁵) will be added to the frequency table. This analysis is considered to be exploratory.

The modified (5 domain) NPC-CSS score will also be presented descriptively including change from baseline values (Visit 9 versus Visit 7). This modified score will range between 0 and 25. If collected, data at Visit 1 of the parent study will also be included.

In addition, a spaghetti plot presenting the total modified (5-domain) NPC-CSS scores of each patient through time will be created.

⁴ Cortina-Borja et al. Annual severity increment score as a tool for stratifying patients with Niemann-Pick disease type C and for recruitment to clinical trials. *Orphanet Journal of Rare Diseases* (2018) 13:143.

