in case all tests were imputed because of missing values, no SCAFI score will be determined. This contradicts the “SCAFI rating manual”.

SARA

The overall SARA score is reported as provided in the eCRF. For presentation of the subscore results, the individual results as provided in the eCRF will be used, where for the subscores finger chase, nose-finger test, fast alternating hand movements, heel-shin slide this is the average value for the two sides (left and right) as determined per eCRF.

mDRS

The mDRS composite score (only relevant for the Parent Study) is calculated as a sum of the separate subscores divided by 24. If one of the subscores is missing, the mDRS composite score is missing as well. As compared to the official questionnaire, the eCRF allows values of 0 (“normal”) for the subscores.

Modified NPC-CSS and ASIS

The modified (15 domain) NPC-CSS total score is calculated as the sum of the 8 major and the 7 modifier scores, and ranges from 0-54. This is referred to as the (15 domain) NPC-CSS sum/total score. The modified (5 domain) NPC-CSS consists of the domains for Ambulation, Cognition, Fine motor, Speech and Swallowing. The ASIS score is obtained by dividing the total (15 domain) NPC-CSS severity score of a patient by the age of the patient at Visit 9, providing a measure of the rate of disease progression in individual patients. The modified (15 domain) NPC-CSS total score, the modified (5 domain) NPC-CSS score and the ASIS score are all only relevant for the Extension Phase.

If one of the NPC-CSS subscores is missing, the total sum scores will be missing as well and so will the ASIS score.

Durations, determination of baseline values and handling of missing data will be programmed as stated in the respective analysis sections.

Laboratory

Laboratory safety data measurements that are denoted as smaller/larger than a certain value (e.g. < x.x), will be imputed with this value (e.g. x.x) for calculations of descriptive statistics. Listings will show the value as collected, and a footnote will be added to the summary tables for explanation.

Comments

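### The Extension Phase primary analysis scores a missing 12-month NPC-CSS on the 6-month visit, tests it against a 12-month null of 10%, and prespecifies no alternative success rate.

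*SAP*

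**What the plan says.** SAP 6.6.1 defines the endpoint: "Success is defined as no change or a decrease in the 5-domain NPC-CSS score from Visit 7 to Visit 9". The success proportion is compared with 0.10 by a one-sided Fisher's Exact Test and reported with a p-value and an exact 90% confidence interval. The 10% comes from Protocol Appendix 6, 8.5.1, which postulates that under standard of care "90% of patients would worsen (higher score) in terms of their performance in 5-domain NPCS-CSS scale over a 12-month period".

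For a missing Visit 9 score, SAP 6.6 applies last observation carried forward (LOCF): "For the primary endpoint 5-Domain NPC-CSS this implies that the measurement of Visit 8 will be used instead". Protocol Appendix 6, 8.6 has the same rule: "this implies that the score of Visit 8 will be used instead". Both sections then exclude sensitivity analyses. SAP 2.2.2 places Visit 8 at about Day 180 and Visit 9 at about Day 365, each within 14 days. Missingness is not confined to withdrawals, because SAP 10.1 says: "If one of the NPC-CSS subscores is missing, the total sum scores will be missing as well".

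The analysis sets differ between the documents. Protocol Appendix 6, 8.1.2 requires Visit 7 and Visit 9 scores for the mITTe and the PPSe. Its ITTe requires an extension dose and a Visit 7 score. Protocol Appendix 6, 8.5 plans a supplementary PPSe analysis. SAP 3.2.1 gives the name mITTe to a set with the protocol's ITTe definition, and SAP Section 7 removes the ITTe and the PPSe.

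**The concern.** The outcome and its benchmark share a 12-month window. A patient scored at Visit 8 has had about half of that time in which to worsen, but is still compared with the 12-month 10%. In a progressive disease, where success means no worsening, fewer patients may have worsened by 6 months than by 12. The substitution then leans towards success: the estimated rate is too high and, depending on the sample size, the one-sided test can exceed 5%.

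The protocol's PPSe analysis used only patients with a Visit 9 score, and the SAP drops it. The reported success rate, p-value and interval then all depend on the Visit 8 rule.

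**Working it through.** **Inputs.** Null 0.10 (SAP 6.6.1, with the 12-month basis in Protocol Appendix 6, 8.5.1); one-sided 5% (SAP 6.1); n=20 and an alternative of 31% (SAP 2.4.2). Rollover, from the same section: "The expectation is that between 60% and 70% of patients will rollover into the extension period". For 32 patients this is 0.60×32=19.2 to 0.70×32=22.4, so 20, 21 or 22 whole patients.

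**Assumptions.** The documents do not give k, the number of patients scored on Visit 8, or q, the 6-month success rate under the null. Missingness is taken as unrelated to outcome. The SAP names Fisher's Exact Test against a fixed proportion; the calculations below use the exact one-sample binomial test in its place.

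**The plan's own figure.** The smallest cut-off c with P(X≥c)≤0.05 for Binomial(20, 0.10) is 5, with exact level 0.0432. Power at 31% is P(X≥5)=0.791, which agrees with the stated 80%.

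**Level with substitutions, n=20.** The number of successes is the sum of Binomial(20−k, 0.10) and Binomial(k, q).

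- k=1: (1−q)·P(B19≥5) + q·P(B19≥4) = 0.0352 + 0.0798q.
- k=2: (1−q)²·0.0282 + 2q(1−q)·0.0982 + q²·0.2662.

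Under a constant hazard with no recovery, a 12-month rate of 10% implies q=√0.10=0.316.

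| q | k=1 | k=2 |
|---|---|---|
| 0.10 | 4.3% | 4.3% |
| 0.20 | 5.1% | 6.0% |
| 0.316 | 6.0% | 8.2% |

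The level passes 5% when q exceeds 18.5% for k=1 [(0.05−0.0352)/0.0798] or 14.2% for k=2.

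**Other planned sizes.** At n=21 and n=22 the cut-off rises to 6, with exact levels of 1.4% and 1.8%. For k=2 and q=0.316:

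- n=21: 0.4675×0.0086 + 0.4325×0.0352 + 0.10×0.1150 = 0.031.
- n=22: 0.4675×0.0113 + 0.4325×0.0432 + 0.10×0.1330 = 0.037.

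Two substitutions pass 5% only when q is above 51.4% (n=21) or 43.5% (n=22).

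**Bias in the estimate under the null.** This is k(q−0.10)/n. For k=2 and q=0.316 it is 2×0.216/20=2.2 percentage points at n=20, 2.1 at n=21 and 2.0 at n=22. At n=20 with q=0.20 it is 1.0 point.

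**What one patient can do at n=20.** Five successes in 20 give p=0.043. If one of them came from Visit 8, the same data give p=0.133 when that patient is counted as a non-success (4/20), and p=0.115 in the observed cases (4/19).

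**The case against.** **Status.** SAP 6.1 and 6.6.1 call the analysis exploratory, and SAP Section 7 lets only the Parent Study primary endpoint decide trial success. This stands. A reader might infer that the trial's conclusion is at risk, and the documents do not support that.

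**Level.** A reader might infer that the test generally exceeds 5%. It does so in the low-substitution cases mainly at n=20, where the discrete test sits closest to its limit. The values of q and k are assumed. The constant-hazard case also excludes recovery, although the success definition allows a decrease in score. With no missing Visit 9 scores, or q=0.10, there is no bias. Nor is a carried-forward score an automatic success: a patient already worse at Visit 8 is scored as a failure.

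**Transparency.** A reader might infer that the rule could not be checked at all. That is too strong. The SAP plans descriptive Visit 9 versus Visit 7 change, a spaghetti plot of 5-domain scores and individual listings (6.6, 6.6.1, 12.3, 12.4), so a recount is possible in a set of about 20. What is not prespecified is any alternative success rate, p-value or interval.

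**Parent Study comparison.** SAP 5.6 tests the Parent Study's own LOCF rule with a less favourable value: "then the value -1 (worsening) will be used instead of 0 for the CI-CS for Visit 4 to Visit 6". SAP Section 7 deliberately confines this to the Parent Study primary analysis, so its absence here is a choice and not an oversight. It does show that the sponsor has accepted this kind of check.

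**Both visits missing.** Carrying Visit 7 forward would give zero change and hence success. The plan does not say to do this: SAP 6.6 names only Visit 8, and the general wording in SAP 5.3 and 6.1 points towards missing or excluded. Neither section settles it for this tested endpoint, so a clarifying sentence is enough. How Early Termination NPC-CSS scores are used is likewise only a point to clarify.

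**Conclusion.** The concern holds as a bias in a stated rule. Day-180 scores stand in for Day-365 scores against a 12-month benchmark, sensitivity analyses are excluded, and the one supplementary set that required Visit 9 has been removed. If the 6-month null rate exceeds 10%, the success rate is biased upward at every planned size, by about 2 percentage points with two substitutions at 31.6%. At n=20 the test level then rises from 4.3% to 8.2%; at n=21 and 22 it stays below 5% unless the rate or the number of substitutions is higher. These sizes rest on the assumed q and k, on missingness unrelated to outcome, and on the exact binomial test. Because the analysis is exploratory, this is a change that should be made, but it does not threaten the trial's main result.

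**What to change.** Keep Visit 8 LOCF as the primary analysis. In SAP 6.6, and in Protocol Appendix 6, 8.6 if it is amended, delete the exclusion of sensitivity analyses for this endpoint. Then:

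- Prespecify the success rate, p-value and confidence interval with mITTe patients lacking a Visit 9 5-domain score counted as non-success, and an observed-case result alongside.
- Report the number of patients scored on Visit 8.
- State that Visit 7 is not carried forward as a success when Visits 8 and 9 are both missing.
- Record in SAP Section 7 that the SAP mITTe uses the protocol's ITTe definition. The protocol mITTe requires a Visit 9 score and would leave LOCF nothing to impute.

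The cost is SAP wording, one Section 7 entry and two result rows, with no new data. The primary analysis keeps its 79.1% power. The downside is a possibly less favourable figure. The non-success analysis is conservative: it also fails a patient with a single missing domain, and at a 31% success rate and n=20 its power is 74.9%, 70.0% or 64.5% with one, two or three missing scores. It therefore belongs beside the observed-case result as a sensitivity analysis and should not replace the primary.
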